### 12.4.1.1. Study Phases for Concomitant Medication

Study Phase	Definition Note: All programming should use start and end dates where available, CMSTRF and CMENRF are only to be used where dates are unavailable to help determine the correct study phase.
Pre-treatment	
 
Conmed Start Date < Study Treatment First Dose Date
 
Conmed End Date < Study Treatment First Dose Date
 
CMSTRF = "BEFORE"
 
Randomisation date is missing i.e. subject was not randomised
 

On-treatment	
 
Study Treatment First Dose Date <= Conmed Start Date <= Study Treatment Last Dose Date + 28
 
Study Treatment First Dose Date <= Conmed End Date <= Study Treatment Last Dose Date + 28
 
(Conmed Start Date <= Study Treatment Last Dose Date + 28) and (Conmed End Date >= Study Treatment First Dose Date)
 
(Conmed Start Date <= Study Treatment Last Dose Date + 28) and (CMENRF = "DURING/AFTER" or CMENRF = "AFTER" or CMSTRF = "DURING")
 
(CMSTRF = "BEFORE" or CMSTRF = "DURING" or CMENRF = "DURING/AFTER") and (Conmed End Date >= Study Treatment First Dose Date)
 
(CMSTRF = "BEFORE" or CMSTRF = "DURING") and (CMENRF = "DURING/AFTER" or CMENRF = "AFTER")
 
CMSTRF = "DURING"
 
CMENRF = "DURING/AFTER"
 

Post-treatment	
 
Conmed Start Date > Study Treatment Last Dose Date + 28
 
Conmed End Date > Study Treatment Last Dose Date + 28
 
CMENRF = "AFTER"
 
CMENRF = "DURING/AFTER"
 

All phases	
 
Conmed start date is missing and CMSTRF is missing and conmed end date is missing and CMENRF is missing
 

#### 1. NOTES:

- The duration of a single concomitant medication can extend over multiple study phases
- Please refer to [Appendix 7: Reporting Standards for Missing Data](#) for handling of missing and partial dates for concomitant medication. Use the rules in this table if concomitant medication date is completely missing.

### 12.4.2. Treatment Emergent Flag for Adverse Events

Flag	Definition
Treatment Emergent	
If AE onset date is on or after treatment start date & on or before treatment stop date + 28 days.
 
Study Treatment Start Date ≤ AE Start Date ≤ Study Treatment Stop Date + 28 days

#### NOTES:

- If the study treatment stop date is missing then the AE will be considered to be On-treatment.

## 12.5. Appendix 5: Data Display Standards & Handling Conventions

### 12.5.1. Reporting Process

Software	

 
The currently supported versions of SAS software will be used.
 
	
Reporting Area	
HARP Server	: uk1salx00175
HARP Compound	: /arprod/gsk3772847/mid207597/

Additional information of reporting areas:
 
data_look_01 This is where the blinded dry run will take place.
 
final_01: This is where the end of treatment phase analysis will take place.
 
final_02: This is where the end of study analysis will take place.
 
Details of the reporting efforts used for the iSRC analysis are detailed in the separate iSRC RAP.
	
Analysis Datasets	

 
Analysis datasets will be created according to CDISC standards
 
	
Generation of RTF Files	

 
RTF files will be generated for all reporting efforts
 
	

### 12.5.2. Reporting Standards

General

 
The current GSK Integrated Data Standards Library (IDSL) will be applied for reporting, unless otherwise stated (IDSL Standards Location: https://spope.gsk.com/sites/IDSLLibrary/SitePages/Home.aspx):             
 
4.03 to 4.23: General Principles
 
5.01 to 5.08: Principles Related to Data Listings
 
6.01 to 6.11: Principles Related to Summary Tables
 
7.01 to 7.13: Principles Related to Graphics
 
 
 
Do not include subject level listings in the main body of the GSK Clinical Study Report. All subject level listings should be located in the modular appendices as ICH or non-ICH listings
 

Formats

 
GSK IDSL Statistical Principles (5.03 & 6.06.3) for decimal places (DP's) will be adopted for reporting of data based on the raw data collected, unless otherwise stated.
 
Numeric data will be reported at the precision collected on the eCRF.
 

 
The reported precision from non eCRF sources will follow the IDSL statistical principles but may be adjusted to a clinically interpretable number of DP's.
 
	
Planned and Actual Time	

 
Reporting for tables, figures and formal statistical analyses:                             
 
Planned time relative to dosing will be used in figures, summaries, statistical analyses and calculation of any derived parameters, unless otherwise stated.
 
The impact of any major deviation from the planned assessment times and/or scheduled visit days on the analyses and interpretation of the results will be assessed as appropriate.
 
 
 
Reporting for Data Listings:                             
 
Planned and actual time relative to study drug dosing will be shown in listings (Refer to IDSL Statistical Principle 5.05.1).
 
Unscheduled or unplanned readings will be presented within the subject's listings.
 
 
 
	
Unscheduled Visits	

 
Unscheduled visits will not be included in summary tables and/or figures.
 
All unscheduled visits will be included in listings.
 
	
Descriptive Summary Statistics	
Continuous Data	Refer to IDSL Statistical Principle 6.06.1
Categorical Data	N, n, frequency, %
Graphical Displays	

 
Refer to IDSL Statistical Principals 7.01 to 7.13.
 
	

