## 5.2. Baseline Definitions

For all endpoints (except as noted in baseline definitions) the baseline value will be the latest pre-dose assessment with a non-missing value, including those from unscheduled visits.

Parameter	Study Assessments Considered As Baseline			Baseline Used in Data Display
	Pre-Screening	Screen Run-in	Day 1 (Pre-Dose)	
Loss of Asthma Control				
Pre-bronchodilator Forced expiratory volume in 1 second (FEV 1 )		X	X	Day 1
Asthma Control Questionnaire (ACQ-5) score		X	X	Day 1
Other Patient Reported Outcomes				
St. George's Respiratory Questionnaire (SGRQ)			X	Day 1
Peak Expiratory Flow (PEF)				
Mean morning peak expiratory flow (PEF)		X	X	Run-in [1]
Mean evening peak expiratory flow (PEF)		X	X	Run-in [1]
Fractional Exhaled Nitric Oxide (FeNO)				
Fractional Exhaled Nitric Oxide (FeNO)			X	Day 1
Symptom Scores				
Mean daytime asthma symptom score		X	X	Run-in [1]
Night-time awakenings due to asthma symptoms requiring rescue medication		X	X	Run-in [1]

Parameter	Study Assessments Considered As Baseline			Baseline Used in Data Display
	Pre- Screening	Screen Run-in	Day 1 (Pre-Dose)	
Rescue Medication				
Rescue medication use		X	X	Run-in [1]
Mean number of inhalations per day over each four weeks		X	X	Run-in [1]
Safety				
Vital Signs		X	X	Day 1
12-lead Electrocardiogram (ECG) measurements		X	X	Day 1
24 hours Holter measurements		X		Screen/Run in
Clinical laboratory tests (haematology and chemistry)		X	X	Day 1
Biomarkers				
Induced sputum biomarkers			X	Day 1
Serum biomarkers			X	Day 1
Exploratory serum markers			X	Day 1

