

Rate of Events per 1000 Treatment Years
 
Rate of events per 1000 treatment years will be calculated using:
 
Rate = number of events * 1000 / total treatment exposure in years where subjects can contribute more than one event.
 
This is equivalent to: Rate = number of events * 1000 / (number of subjects in treatment group * mean treatment exposure in years).

--

Maximum/Minimum Definitions for Vital Signs Data
 
Maximum and Minimum: Maximum and Minimum post-randomisation value over all time-points (including scheduled and unscheduled assessments) will be presented.

---

FEV1

Absolute Reversibility
 
Absolute reversibility (mL) = (post-bronchodilator FEV1 – pre-bronchodilator FEV1)

Percent Reversibility
 
Definition of Percentage Reversibility as a percentage of predicted FEV1 = ((post-bronchodilator FEV1– pre-bronchodilator FEV1) / predicted FEV1) x 100%
 
Definition of Percentage Reversibility as a percentage of pre-bronchodilator FEV1 = ((post-bronchodilator FEV1– pre-bronchodilator FEV1) / pre-bronchodilator FEV1) x 100%

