3.16.	SAFF_ALL	AE1	Summary of On-treatment Adverse Events of Special Interest	IDSL	ETP, SAC
3.17.	SAFF_ALL	AE1	Summary of On-treatment Serious Adverse Events of Special Interest	IDSL	ETP, SAC
3.18.	SAFF_ALL	AE1	Summary of Post-treatment Adverse Events of Special Interest	IDSL	ETP, SAC
3.19.	SAFF_ALL	AE1	Summary of Post-treatment Serious Adverse Events of Special Interest	IDSL	ETP, SAC
Mexico Specific Tables					
3.20.	SAFF_ALL		Summary of Suspected Investigational Product Adverse Reaction (Mexican Participants Only)		ETP, SAC
3.21.	SAFF_ALL		Summary of Suspected Investigational Product Adverse Reaction (Non-Mexican Participants)		ETP, SAC

Safety: Tables					
No.	Population	IDSL / Example Shell	Title	Programming Notes	Deliverable [Priority]
Laboratory: Chemistry					
3.22.	SAFF_ALL	LB1	Summary of Clinical Chemistry	ICH E3	ETP, SAC
3.23.	SAFF_ALL	LB1	Summary of Change from Baseline in Clinical Chemistry	ICH E3	ETP, SAC
3.24.	SAFF_ALL	LB16	Summary of Worst Case Chemistry Results Relative to Normal Range Post-Baseline Relative to Baseline	ICH E3	ETP, SAC
Laboratory: Hematology and Cardiac Markers					
3.25.	SAFF_ALL	LB1	Summary of Hematology and Cardiac Markers	ICH E3	ETP, SAC
3.26.	SAFF_ALL	LB1	Summary of Changes from Baseline in Hematology and Cardiac Markers	ICH E3	ETP, SAC
3.27.	SAFF_ALL	LB16	Summary of Worst Case Hematology and Cardiac Markers Results Relative to Normal Range Post-Baseline Relative to Baseline	ICH E3	ETP, SAC
Laboratory: Hepatobiliary (Liver)					
3.28.	SAFF_ALL	LIVER1	Summary of Liver Monitoring/Stopping Event Reporting	IDSL	ETP, SAC
3.29.	SAFF_ALL	LIVER10	Summary of Hepatobiliary Laboratory Abnormalities	IDSL	ETP, SAC
ECG					
3.30.	SAFF_ALL		Summary of Antihistamine, Decongestant and Caffeine Use Prior to ECG assessments		ETP, SAC
3.31.	SAFF_ALL	EG1	Summary of ECG Findings	IDSL	ETP, SAC
3.32.	SAFF_ALL	EG2	Summary of ECG Values by Visit	IDSL	ETP, SAC

Safety: Tables					
No.	Population	IDSL / Example Shell	Title	Programming Notes	Deliverable [Priority]
3.33.	SAFF_ALL	EG2	Summary of Change from Baseline in ECG Values by Visit	IDSL	ETP, SAC
3.34.	SAFF_ALL	EG10	Summary of Maximum QTcF Values Post-Baseline Relative to Baseline by Category	IDSL	ETP, SAC
3.35.	SAFF_ALL	EG11	Summary of Maximum Increase in QTcF Values Post-Baseline Relative to Baseline by Category	IDSL	ETP, SAC
Holter					

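### The blanket exclusion of unscheduled visits from summary tables contradicts the vital-signs maximum/minimum rule and limits the worst-case laboratory, hepatobiliary and maximum-QTcF tables to scheduled visits

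*SAP*

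**What the plan says.** Table numbers below are those of the amended plan.

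- **General rule (Section 12.5.2, Unscheduled Visits).** "Unscheduled visits will not be included in summary tables and/or figures". The companion bullet reads "All unscheduled visits will be included in listings". Neither is limited to by-visit displays.
- **Company standards (Section 12.5.2, General).** The sponsor's display library "will be applied for reporting, unless otherwise stated".
- **Vital signs (Section 12.6.4).** "Maximum and Minimum post-randomisation value over all time-points (including scheduled and unscheduled assessments) will be presented".
- **Baseline (Section 5.2).** The latest non-missing pre-dose value is used, "including those from unscheduled visits".
- **Planned displays (Section 12.10.7).** Table 3.24 is "Summary of Worst Case Chemistry Results Relative to Normal Range Post-Baseline Relative to Baseline", and Table 3.27 is its counterpart for haematology and cardiac markers. Table 3.29 is "Summary of Hepatobiliary Laboratory Abnormalities". Table 3.34 is "Summary of Maximum QTcF Values Post-Baseline Relative to Baseline by Category", and Table 3.35 is the matching table for the maximum increase. None has a programming note admitting unscheduled values.
- **Laboratory classes (Section 12.8).** Thresholds of potential clinical importance are not used. Results are classed Low, Normal or High against the reference range.

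**The concern.** Leaving unscheduled visits out of a by-visit summary is ordinary practice, because they have no column to go in. A worst-case or maximum table is different: it reports one extreme value per participant, and its title promises that value over the whole post-baseline period. If the source is cut to scheduled visits, the table may not hold what its title says.

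Section 12.6.4 adopts the inclusive rule for vital signs, so the plan contradicts itself there. It gives no such rule for laboratory, liver and QTcF extremes. At stake are the by-arm counts for hepatic, laboratory and QTcF abnormalities in a trial where cardiovascular safety is a special-interest category (Section 12.6.4) and liver monitoring has its own display.

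**Working it through.** The plan gives no figure to reproduce here. The check is to read the rules together and follow what each table would contain.

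**1. Can a company shell override the exclusion?** The library applies only where the plan is silent, and Section 12.5.2 is not silent. Whatever the LB16, LIVER10, EG10 and EG11 shells assume, the explicit rule takes precedence.

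**2. Does another section of the plan override it?**
- Section 12.6.4 does so for the vital-signs maximum and minimum only.
- Section 12.6.1 counts High and Low results at any post-baseline visit but does not mention unscheduled visits, so it does not clearly override the exclusion.
- Section 12.7.1 puts the available planned data of withdrawn participants into tables, which points towards scheduled data.

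**3. Which dates can feed the tables?** From Sections 8.3, 8.4 and 12.2.1:
- Chemistry, including liver chemistry: Weeks 2, 4, 8, 12, 16 and 28. The gaps are 2 weeks up to Week 4, then 4 weeks up to Week 16, then 28 − 16 = 12 weeks, or 12 × 7 = 84 days.
- Haematology and cardiac markers: Weeks 1, 2, 4, 6, 8, 10, 12, 14, 16 and 28. Gaps are at most 2 weeks up to Week 16, followed by the same 84 days.
- ECG: before and after dosing at Weeks 0, 4, 8 and 12, then Week 16. None is scheduled in follow-up.

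**4. Which way can the error go?** For one participant, let S be the scheduled and U the unscheduled post-baseline values. Then max(S) ≤ max(S and U together). With baseline fixed, the same holds for the maximum increase. Dropping U can therefore leave the reported maximum unchanged or lower it, never raise it.

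**5. When does it change a count?**
- *Tables 3.24 and 3.27.* A participant High at a scheduled visit and higher still on an unscheduled repeat is High either way, so nothing changes. A participant within range at every scheduled visit, and High only on an unscheduled sample (say between Weeks 16 and 28), is counted as not High. The same logic applies to Low.
- *Tables 3.34 and 3.35.* These are by category. If the scheduled maximum falls in one category and an unscheduled ECG in a higher one, the participant is counted in the lower.
- *Table 3.29.* If the display grades abnormalities by threshold, an unscheduled liver value that crosses a threshold no scheduled value reached is missed.

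**6. What remains elsewhere?** Every unscheduled value is listed. Liver monitoring and stopping events are summarised in Table 3.28. Cardiac disorders reported as adverse events appear in Tables 3.16 to 3.19. None of these puts the missing value into the five tables.

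**The case against.** The strongest reply is that little is lost.

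- With only Low, Normal and High classes, a participant retested because a scheduled result was High is already counted in Tables 3.24 and 3.27. **This stands**, and it confines the effect on those tables to sole unscheduled out-of-range values.
- Visit 11 doubles as the early-withdrawal visit and includes chemistry and an ECG, and Section 12.7.1 allows withdrawal visits into summaries. Participants who stop treatment therefore have a planned assessment. **This stands** in part: that assessment need not catch the peak.
- Table 3.28 and the special-interest tables summarise some of the same signals by arm. **This stands**, so it would be wrong to say that all such signals survive only in listings. Nor is Table 3.28 shown to be affected, since its title concerns reported events rather than visit values.
- Section 12.6.1 could be read inclusively. It could, but it does not say so, whereas Section 12.6.4 spells the inclusion out for vital signs. Two programmers could reasonably differ.
- The shells are not shown, so the grading in Tables 3.29, 3.34 and 3.35 is known only from their titles. **This stands** as a limit on certainty.

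A reader might infer that hepatic and cardiac harm would be understated in just those participants who had a signal and were retested. The documents do not support this in general: it fails for a retest after a scheduled High, and that peaks fall on repeat tests is a reasonable inference rather than something the plan states.

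A reader might also put a size on it from 70 per arm (1/70 = 1.4 percentage points per participant). But 70 is the evaluable number in the sample-size section. These tables use the safety population including GCP non-compliant participants, whose size is not given.

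Finally, admitting unscheduled values at baseline (Section 5.2) is a separate choice. The different treatment after baseline is untidy but not in itself an error.

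**Conclusion.** The point holds in a limited form. Sections 12.5.2 and 12.6.4 contradict each other on vital-signs extremes. Followed as written, Section 12.5.2 also restricts Tables 3.24, 3.27, 3.29, 3.34 and 3.35 to scheduled visits.

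For Tables 3.34 and 3.35, and for Table 3.29 so far as it is graded, a higher unscheduled value can be missed. For Tables 3.24 and 3.27 the loss is confined to participants whose out-of-range values in a given direction were all unscheduled. The longest window for that is the 84 days between Weeks 16 and 28; for ECGs it is the whole of follow-up.

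Per participant the error can only lower a maximum or leave it alone. Its frequency and its effect on the comparison between arms cannot be quantified from the document. The conclusion assumes that unscheduled laboratory samples or ECGs are taken at all, and that programmers apply Section 12.5.2 literally. It should be corrected because the tables would not reliably contain what their titles promise and the plan already has the right wording for vital signs.

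**What to change.** Replace the first bullet under Unscheduled Visits in Section 12.5.2 with:

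*Unscheduled visits will not be included in by-visit summaries. Worst-case, maximum/minimum, any-visit-post-baseline and abnormality tables (3.24, 3.27, 3.29, 3.34, 3.35) will use all scheduled and unscheduled post-baseline assessments, as for vital signs in 12.6.4.*

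This removes the conflict with Section 12.6.4 and settles the reading of Section 12.6.1. The listings rule stays as it is, and Table 3.28 needs no change on this ground. The cost is one sentence and a small programming change to the source records for five tables. No new data are needed and no efficacy analysis changes. The only visible consequence may be slightly higher abnormality counts.

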## 12.6. Appendix 6: Derived and Transformed Data

### 12.6.1. General

Multiple Measurements at One Analysis Time Point

 
• Mean of the measurements will be calculated and used in any derivation of summary statistics but if listed, all data will be presented.
 
• Participants having both High and Low values for Normal Ranges at any post-baseline visit for safety parameters will be counted in both the High and Low categories of “Any visit post-baseline” row of related summary tables.
 

Study Day

 
• Calculated as the number of days from First Dose Date:             
 
• Ref Date = Missing → Study Day = Missing
 
• Ref Date < First Dose Date → Study Day = Ref Date – First Dose Date
 
• Ref Date ≥ First Dose Date → Study Day = Ref Date – (First Dose Date) + 1
 
 
 

### 12.6.2. Study Population

Age
Date of birth will be set as PPD YYYYY where YYYYY is the year of birth taken from the CRF. For participants who attended a screening visit, age will be calculated at the screening visit date. For pre-screen failures, age will be calculated at the pre-screening visit date.
Body Mass Index (BMI)
BMI = Weight (kg) / Height(m) 
Treatment Misallocations
To allocate treatment, the number of doses of GSK3772847 and Placebo that were given will be calculated, and the subject will be assigned to whichever treatment has the higher number. The only exception will be when both treatments were given equally, in which case the subject will be assigned their randomised treatment.
Early Withdrawal from Study Treatment Date

The eCRF captures the study treatment start and end, however this is the physical time and date of the infusion. The date of early withdrawal from study treatment is not captured and should therefore be calculated as follows:
 
 
• If the participant withdrew from treatment due to loss of asthma control then the date of early withdrawal from study treatment is set to the date of loss of asthma control.
 
• If the participant withdrew due to an AE/SAE/Death then withdrawal date is set to the AE/SAE onset date (all deaths should be reported as serious adverse events)
 
• If the participant withdrew from study treatment (for a reason other than those above) during the first 10 weeks of the study i.e. during the down titration of the background medications, then the FP/SAL or FP discontinuation date should be used as the date of withdrawal from study treatment.
 
• For participants who withdraw from study treatment (for a reason other than those above) between Week 10 and Week 16, there is no information on when they withdrew as they are no longer taking background medications. The date of early withdrawal from study treatment should therefore be set to the maximum of date of last dose of FP and date of last dose +1. This is because no more information is available other than the fact that they had not lost control prior to completing the down titration or prior to receiving their final dose of IP.
 

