## 2.4. Study Design

Overview of Study Design and Key Features	
 
The diagram illustrates the study design timeline from Week 0 to Week 28. It is divided into a Treatment Phase (Weeks 0-12) and a Follow Up Phase (Weeks 16-28). In the Treatment Phase, participants receive a double-blind study treatment every 4 weeks, either GSK3772847 or Placebo, at Weeks 0, 4, 8, and 12. Simultaneously, background therapy is reduced from LABA, Sal, and ICS at Week 0 to FP 500 BID at Week 2, and then further reduced to FP 250 BID, FP 100 BID, and FP 50 BID by Week 10. In the Follow Up Phase, participants receive LABA and ICS from Week 16 to Week 28. Visits are labeled V0 through V14, with an ETP Visit at Week 11.
	
Design Features	
 
The study is a Phase IIa, multicenter, randomised, placebo-controlled, double-blind, stratified, parallel group study.
 

Dosing	
 
Participants will have a two-week Run-in period in which they take a background therapy of fluticasone propionate (FP)/salmeterol 500/50 mcg BID.
 
Following run-in they will be randomised to receive four doses of either GSK3772847 or Placebo intravenously (Week 0, 4, 8 and 12) whilst initially still receiving background FP/Salmeterol 500/50 mcg BID.
 
At Week 2 background therapy will be changed to FP 500 mcg BID only. This will then be reduced by approximately 50 % every two weeks until complete FP discontinuation at Week 10.
 

Treatment Assignment	
 
Participants will be randomised in a 1:1 ratio to receive four doses of either GSK3772847 or Placebo administered intravenously every 4 weeks.
 
Randomisation will be stratified based on participants' baseline peripheral blood eosinophil count which is measured at screening (<150 cells/<math>\mu</math>L, <math>\geq</math>150 cells/<math>\mu</math>L), Randomisation will also be stratified according to whether participants consent to the sputum sub study.
 

Overview of Study Design and Key Features	

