#### 7.1.4. Strategy for Intercurrent (Post-Randomisation) Events

Intercurrent Event	Primary Estimand	Secondary Estimand
Study treatment discontinuation due to an AE/SAE	Excluded from analysis	Set as loss of asthma control (i.e. worst case scenario).
Death	Excluded from analysis	Set as loss of asthma control (i.e. worst case scenario).
Prohibited/ Concomitant medications that could impact patients' asthma control	Use data as is.	Set as loss of asthma control (i.e. worst case scenario).
Non-compliance with FP/SAL, FP or study titration	Use data as is.	Set as loss of asthma control (i.e. worst case scenario).
Missing data *	Excluded from analysis	Set as loss of asthma control (i.e. worst case scenario).
Notes:		

 
• * Missing data is not an intercurrent event, however missing values will be imputed according to the estimand under investigation.
 
		

- |  |
|--|
| 
 
• If the intercurrent event occurs after loss of asthma control then all information on loss of asthma control will be used.
 
• Prohibited/ concomitant medications will be identified as protocol deviations within the prohibited/ concomitant medications category and will have text that start with “LoAC”
 
• Non-compliance FP/SAL, FP or study titration will be identified as compliance <80%, compliance ≥ 120% or protocol deviations within the other deviations related to wrong study treatment/administration/dose sub-category and will have text that starts with “TIT”
 
 |
|--|

If any of the following intercurrent events occurs, then all data will be accepted:

- Pregnancy  
Accidental unblinding

Whilst it’s possible that site staff were unable to administer study drug as they were unable to find a suitable vein, the team felt this would not be caused by the randomised study treatment and the visit would be rescheduled. Therefore, if this occurs all data will be accepted and treated as any other out of window assessment.

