**7.2.3. Strategy for Intercurrent (Post-Randomisation) Events**

For the analysis of time to loss of asthma control, both primary and secondary estimands (Section 7.1.4) will be examined. It is important to assess both estimands as data is missing after withdrawal or loss of asthma control. This could produce biased estimates, as loss of control and therefore missing data is related to study treatment, and so the secondary estimand where missing data is set as non-responders must also be considered.

For all other endpoints, only the primary estimand will be examined. This estimand uses all data as collected, except for data collected after the date of loss of asthma control or early withdrawal from study treatment.

Once participants experience loss of asthma control and/or withdraw from study treatment they immediately restart their standard of care medication (ICS/LABA). As a

result, any data collected past this point will have been impacted by the standard of care medications and any estimates produced biased by the additional use of ICS/LABA. For this reason, data post withdrawal from study treatment is not included in the on-treatment efficacy analysis.

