**7.2.4.1. Statistical Methodology Specification**

Endpoint / Variables

 
Time to loss of asthma control.
 

Strategy for Intercurrent (Post-Randomisation) Events

 
Both primary and secondary estimands (Section 7.1.4) will be examined. It is important to assess both estimands as data is missing after withdrawal or loss of asthma control. This could produce biased estimates, as loss of control and therefore missing data is related to study treatment, and so the secondary estimand where missing data is set as non-responders must also be considered.
 

Model Specification

 
Time to loss of asthma control will be analysed on the Modified Intent-to-Treat excluding GCP non-compliant subjects (Loss of Control) population using Kaplan-Meier analysis (Proc lifetest). Within the Kaplan Meier plot participants will either be counted as an event or they will be censored.
 
A log rank test will be performed to test for difference between the time to loss of asthma control on Placebo compared with GSK3772847
 
 
Primary Estimand:
 
 
Events: Participants who experience loss of asthma control during the study
 
Censoring: Participants who discontinue investigational product for reasons other than loss of asthma control will be censored at the date of early withdrawal from study treatment. Participants who successfully complete the 16 week treatment period will be censored at 113 days (16 weeks + 1 day).
 
 
Secondary Estimand:
 
 
Events: Participants who experience loss of asthma control during the study or who discontinue investigational product for reasons other than loss of asthma control (date of event will be set to date of early withdrawal from study treatment).
 
Censoring: Participants who successfully complete the 16 week treatment period will be censored at 113 days (16 weeks + 1 day).
 

Time to event/censoring = Date of event/censoring – Treatment start date + 1. If participants experience multiple reasons for loss of control then the earliest date will be used as described in Section 0.

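### For adverse-event withdrawals the derived early-withdrawal date is AE onset with no lower limit, so it can fall before infusions the participant went on to receive

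*SAP*

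**What the plan says.** Section 12.6.2 explains why a derivation is needed: "The date of early withdrawal from study treatment is not captured and should therefore be calculated as follows". Four rules follow, chosen by reason and timing of withdrawal.

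- Loss of asthma control: the date of loss of control.
- AE, SAE or death: "If the participant withdrew due to an AE/SAE/Death then withdrawal date is set to the AE/SAE onset date".
- Any other reason in the first 10 weeks: "then the FP/SAL or FP discontinuation date should be used as the date of withdrawal from study treatment".
- Any other reason between Weeks 10 and 16: "set to the maximum of date of last dose of FP and date of last dose +1".

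The date is then used in three places.

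- In the Kaplan-Meier analysis (section 7.2.4.1), participants who stop for reasons other than loss of control "will be censored at the date of early withdrawal from study treatment" under the primary estimand. Under the secondary estimand they count as events on that date.
- Section 12.4.1 ends the efficacy on-treatment phase at discontinuation for those who stop early.
- Section 7.2.3 excludes efficacy data after that point, for this reason: "Once participants experience loss of asthma control and/or withdraw from study treatment they immediately restart their standard of care medication (ICS/LABA").

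For the loss-of-control proportions, section 7.1.4 excludes AE discontinuations and deaths (primary estimand) or counts them as loss of control (secondary estimand), with this proviso: "If the intercurrent event occurs after loss of asthma control then all information on loss of asthma control will be used".

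**The concern.** An adverse event that ends treatment can begin some time before the decision to stop. Infusions are four weeks apart, so one or more may be given in between. The AE rule sets no floor at the last infusion, and no other section supplies one. Read literally, the plan can date a participant as withdrawn before infusions shown in the dosing record.

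This also conflicts with the plan's reason for cutting the data. Standard ICS/LABA is restarted when treatment actually stops. Between AE onset and that stop, the bias the plan wants to avoid has not yet arisen.

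At stake are the timing in the time-to-loss-of-control curves and log-rank test, the placement of imputed failures in the Weeks 0-6 analysis under the secondary estimand, and some valid on-treatment efficacy values.

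**Working it through.** The SAP gives no figure on this point, so there is nothing to reproduce. The check applies its rules to its own schedule.

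**Inputs from the SAP**
- Infusions at Weeks 0, 4, 8 and 12 (section 2.4), that is Days 1, 29, 57 and 85 (section 12.2.1). The sampling table there prints Day 49 for Week 8. Day 57 is used here, as in the main schedule (8 × 7 + 1 = 57).
- Week 2 is Day 15 and Week 6 is Day 43 (section 12.2.1).
- Time to event or censoring = date − treatment start + 1 (section 7.2.4.1), so the time equals the study day.
- The efficacy post-treatment phase begins after the study treatment stop date + 28 days (section 12.4.1).

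**Assumed:** the AE onset day and the last infusion received.

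**Step 1: one participant.** Onset Day 20, infusions on Days 1, 29 and 57, then withdrawal for that AE.
- Derived date: Day 20, with two infusions after it.
- Last infusion + 1, the convention of the Week 10-16 rule: 57 + 1 = Day 58.
- Gap: 58 − 20 = 38 days. If actual stopping was on Day 70 (assumed), the gap to the true stop is 70 − 20 = 50 days.

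**Step 2: other onset days.** Days by which the derived date precedes last infusion + 1 (last infusion day + 1 − onset day):

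| Assumed onset | Last infusion Day 29 | Day 57 | Day 85 |
|---|---|---|---|
| Day 2 | 28 | 56 | 84 |
| Day 10 | 20 | 48 | 76 |
| Day 20 | 10 | 38 | 66 |
| Day 30 | – | 28 | 56 |
| Day 50 | – | 8 | 36 |
| Day 70 | – | – | 16 |

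The range over these cases is 8 to 84 days. It is zero when no infusion follows onset and onset is later than the last infusion.

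**Step 3: consequences for the Step 1 participant**
- Kaplan-Meier: censored at 20 (primary) or failed at 20 (secondary), when the dosing record supports at least 58.
- Weeks 0-6, secondary estimand: if the imputed failure is placed at the derived date, Day 20 lies inside the window (20 < 43), whereas Day 58 lies outside it.
- Efficacy data: the Week 4, 6 and 8 visits (Days 29, 43 and 57) are dropped. FEV1 is scheduled at Weeks 2 and 4 within the modelled period, so one of its two modelled visits is lost. The FeNO and eosinophil models also lose Week 4, and so does the exploratory Week 4 FEV1 model. With onset on Day 10, Week 2 (Day 15) is lost too.
- Phases: post-treatment starts after 57 + 28 = Day 85, so Days 21 to 85 belong to no efficacy phase. With the date at Day 58, only Days 59 to 85 would be unassigned.

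**Step 4: partial onset dates.** Section 12.7.2.1 sets a missing start day to the first of the month (or to treatment start) and leaves a completely missing date missing. If that convention carries over, the derived date can move earlier still or be undefined.

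**The case against.** The best defence is that the four rules differ because the information differs. The Week 10-16 rule is an explicit fallback for when nothing better is known, not a general floor. The first-10-weeks rule states no floor either. For an AE there is a further recorded date, and the plan uses it. Where no infusion follows onset, onset can be the better evidence. With last FP on Day 71, last infusion on Day 85 and onset on Day 100, the present rule gives Day 100, while the Week 10-16 rule would give Day 86 and discard 14 days of follow-up. That stands, and it rules out simply copying the Week 10-16 rule. It does not defend a date earlier than an infusion already given.

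The limited reach also stands. FEV1, FeNO and eosinophils after Week 4, and ACQ-5, SGRQ and diary endpoints throughout, are descriptive only. Time to loss of control is a secondary endpoint in a Phase IIa trial. How often dosing continues after the onset of the AE that ends treatment depends on recording conventions and stopping rules outside the SAP.

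A reader might go further and infer that genuine losses of control will be removed from the primary estimand, because a back-dated AE would precede them. The SAP does not support that. Section 7.1.4 turns on when the discontinuation occurs and does not say that the derived date decides the order. A withdrawal for loss of control takes the loss-of-control date. The scenario needs a participant who lost control but whose withdrawal was recorded as due to an AE. What remains is a gap: the plan does not say which date settles the order.

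A reader might also infer that adverse-event windows shift. They do not. Sections 12.4.1 and 12.4.2 use the study treatment stop date, a separate item that follows the infusion record.

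**Conclusion.** The defect is real but confined to a derivation. It touches the time-to-loss-of-control analysis under both estimands, the Weeks 0-6 analysis under the secondary estimand, the Week 4 values in three repeated-measures models and one exploratory model, and the descriptive on-treatment summaries. The Weeks 0-16 proportion is largely unaffected, since section 7.1.4 handles AE discontinuations the same way whatever their date.

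For an affected participant the error ran from 8 to 84 days in the cases tried, which rest on assumed onset days and the nominal schedule. The SAP gives no AE withdrawal rate and no basis for the number affected, nor does it show whether they would divide unequally between arms. The correction is worth making because it is specific, cheap and needed only when the dosing record contradicts the derived date.

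**What to change.** Reword the AE/SAE/death rule in section 12.6.2.

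- AE or SAE withdrawal: the latest of the AE/SAE onset date and the last infusion date + 1 and, in the first 10 weeks, also the recorded FP/SAL or FP discontinuation date. For the Step 1 participant this gives Day 58, or the FP discontinuation date if later. For the Day 100 onset case it keeps Day 100.
- Death with no earlier recorded stop: the death date, which section 12.6.2 already uses for exposure.
- Onset date partial or missing: say how it enters the comparison. Last infusion + 1 then bounds the result from below.

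Add one sentence to section 7.1.4 stating that this derived date, not AE onset alone, determines whether an AE discontinuation came before or after loss of control.

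The cost is a few lines of SAP text and one changed derivation, using dates the plan already relies on. It changes data handling only and should be settled before unblinding.
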